10.2.1.1 Primary Analysis

The primary analysis will be performed at the time of the main analysis for ORR as centrally measured by an Independent Review Committee (IRC) based on RECIST 1.1 criteria.

IRC tumor response variables will be measured by 2 independent assessors. A patient will have the same 2 assessors through out the trial. There are in total 4 assessor, named in numerical sequence: ‘Independent Assessor 1’, ‘Independent Assessor 2’, ‘Independent Assessor 5’, ‘Independent Assessor 6’. The Banook Imaging Review Charter ensures categorical tumor response variables will agree between the independent assessors. The continuous tumor size variables can differ between independent assessors. An overall independent assessor analysis value will be derived for use in the primary analysis. The overall independent assessor analysis value for tumor size will be the value from the first alphabetically sorted assessor (e.g. if ‘Independent Assessor 2’ and ‘Independent Assessor 5’, the overall tumor size will be assigned as from ‘Independent Assessor 2’).

The hypothesis tested will be according to the decision taken at the interim analysis:

- Scenario 1: If the ORR homogeneity assumption is met at the end of Stage 1 and futility is not met, then the hypothesis will be:

$$H_0: ORR \leq 15\% \text{ against } H_1: ORR > 15\%$$

The statistical comparison will be conducted on the combined Stage 1 and Stage 2 pooled sample of data across cohorts using a one sided binomial exact test at an alpha level of 5%.

- Scenario 2: If the ORR homogeneity assumption is not met at the end of Stage 1, then a decision will be made at the time of interim analysis to further continue the study with only 1 cohort or multiple cohorts. Then the hypothesis tested at the final stage will be:

$$H_0: ORR \leq 15\% \text{ against } H_1: ORR > 15\% \text{ in each continuing cohort}$$

The statistical comparison will be conducted within each continuing cohort on the combined Stage 1 and Stage 2 pooled sample using a one sided binomial exact test at an alpha level of 5% divided by the number of non-futile cohorts.

As such, the overall family wise error rate (FWER) for the study is controlled under 5%.

However, the interim analysis to examine homogeneity of ORR across cohorts was not conducted after data monitoring review observed a lower than expected antitumor activity in the pooled group. Therefore, the main analysis will present the analysis of ORR (and other efficacy endpoints) by cohort and pooled total subjects.

Objective response rate will be summarized using frequencies and percentages. The Clopper-Pearson CI will be calculated using a one-sided binomial exact test at an alpha level as described in the hypothesis testing will be presented for all stage combined.

The best overall response (CR, PR, SD, PD and NE) will be summarized descriptively to show the number and percentage of subjects in each response category. The PD category will be further split into radiological progression (RECIST) and clinical progression. (Note: In case a patient has both radiological and clinical progression, the patient will be summarized under radiological progression.) The NE category will be further split into SD observed before 6 weeks, incomplete post baseline assessment and death without post-baseline assessment.

10.2.1.2 Supportive Analysis

The analysis on ORR will be repeated on mITT and PP population as supportive analysis.

A sensitivity analysis will also be performed on the ORR based on local investigator assessment of response using RECIST 1.1 criteria. This analysis will be performed using the ITT population and repeated using the mITT and PP populations.

10.2.2 Duration of Response

Duration of response (months) is defined as (date of the first documented disease progression or death due to any cause, whichever occurs first - date of the initial response (PR or CR) + 1)/30.4375. It will be calculated only for subjects with a confirmed BOR of CR or PR.

The following censoring rules will be applied:

- Subjects who do not experience death or PD, nor initiate a new anti-cancer therapy will be right-censored at the date of their last adequate tumor assessment (i.e. a tumor assessment not showing NE).
- Subjects having initiated a new anti-cancer therapy before experiencing death or PD will be right-censored at the date of their last adequate tumor assessment prior to initiation of a new anti-cancer therapy.
- Subjects who experienced death or PD after two or more consecutive missing or inadequate tumor assessments will be right-censored at their latest adequate assessment before death or PD.

Median, 25th and 75th percentile of duration of response with corresponding 95% CI (using log-log transform, Brookmeyer and Crowley 1982) will be provided. Duration of response rate with corresponding 95% CIs (using Greenwood's formula and log-log transform, Kalbfleisch and Prentice 2002) at every 6 months will be presented. A K-M plot for DOR will be presented.

Swimmer plots will be used to graphically present the DOR for each subject with a documented response of CR or PR.

The analysis on DOR will be based on the IRC evaluation on using the ITT population as the main analysis. Supportive analyses will be performed using:

- IRC evaluation of response on mITT and PP populations.
- Investigator assessed response on ITT, mITT and PP populations.

10.2.3 Disease Control Rate

Disease control rate is defined as number of subjects with a BOR of confirmed CR, confirmed PR or SD at least 6 weeks after the date of first dose of the study drug.

Disease control rate will be summarized using frequencies and percentages. In addition, 95% Clopper-Pearson CI will be provided.

The analysis of DCR will be performed based on the independent review committee (IRC) evaluation on the ITT population as the main analysis. Supportive analyses will be performed using:

- IRC evaluation of response on mITT and PP populations.
- Investigator assessed responses on ITT, mITT and PP populations.

10.2.4 Tumor Size

The change in tumor size will be calculated for each subject in the ITT population as the percentage change from baseline in the sum of longest diameters of target tumor lesions at each assessment time point. The percentage change from baseline in the sum of longest diameters will be summarized for each scheduled assessment. In addition, the largest decrease in tumor size or the minimum increase from baseline in the absence of a reduction from baseline based on all post baseline assessments will be summarized descriptively. Waterfall plots will be used to present graphically the largest decrease for each subject by BOR. Reference lines will be drawn at +20% and -30% change from baseline. A waterfall plot will be presented for each cohort and overall.

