## 5. STUDY DESIGN AND TREATMENT

### 5.1. Study Design

This is a multicentre, basket, two stage, adaptive single arm Phase II study to examine the efficacy of Debio 1347 administered at the recommended Phase II dose of 80 mg in subjects with solid tumors harboring FGFR1-3 gene fusion/rearrangement. The study will include 3 cohorts of subjects comprising biliary tract cancer (Cohort 1), urothelial cancer (Cohort 2) and, in Cohort 3, all other solid tumor histologies not included in Cohorts 1-2, such as non small cell lung cancer (NSCLC), head and neck cancer, thyroid cancer, oral cancer, breast cancer, prostate cancer and others but excluding primary brain tumors.

Stage 1 will require 27 evaluable subjects across the three cohorts assuming an equal accrual rate per cohort. Stage 2 will require 86 evaluable subjects across all cohorts or per individual cohort depending on results of assessments scheduled at the end of Stage 1 (see graphical algorithm below and Section 11). Assuming a drop out rate of 10%, up to 125 subjects will be enrolled into the study.

Subjects will be treated with Debio 1347 daily in 28-day cycles until the occurrence of disease progression (clinical or radiologic) or unacceptable toxicity (other treatment discontinuation criteria are described in Section 8.4.1). Subject safety (AEs) and survival will be followed-up respectively for 30 days after the last Debio 1347 dose and every 12 weeks from treatment end until death or loss to follow-up but no longer than for a total of 2 years after the last subject has discontinued treatment. Disease status will be followed-up every 12 weeks only in subjects without PD from treatment end until PD, death or loss to follow-up but no longer than for a total of 2 years after the last subject has discontinued treatment.

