8.4 Handling of Unscheduled Assessments or Retests

In case of pre-dose retests, the latest value will be used in the analysis. The post-dose retests and the unscheduled assessments will not be used in the summary statistics but will be used in the derivation of endpoints that are not related to a specific timepoint (i.e. worst-case assessment, BOR, time to event endpoints, etc.). They will also be displayed in listings.

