10.2.1 Objective Response Rate

Objective response rate (ORR) is defined as the proportion of subjects with a best overall response of confirmed PR or confirmed CR based on RECIST 1.1 criteria.

Best overall response (BOR) is defined as the best response designation for each subject that is recorded between the date of first administration of the study drug and the date of first documented disease progression per RECIST 1.1, the date of non-permitted concomitant treatment, date of a new systemic therapy or the date of study withdrawal for other reason, whichever occurs first.

Stable Disease (SD) will be considered as BOR only if the assessment is performed at least 6 weeks (i.e. 42 days) after the date of first dose of the study drug. If the minimum time from first dose of the study drug is not met when SD is observed, then subject's BOR depends on the subsequent assessments. A subject lost to follow-up after the first SD assessment will be considered not evaluable (NE). Subjects without any radiologic tumor assessment will be considered as NE. Patients who die with no evaluable RECIST assessments will be assigned to the NE category.

Per RECIST 1.1 criteria, CR and PR needs to be confirmed at a subsequent assessment, at least 4 weeks (i.e. 28 days) after initial overall response assessment of CR/PR. Confirmed BOR will be derived as described in RECIST 1.1 guidance summarized in Table 2.

Table 2 - Confirmation of BOR based on RECIST 1.1

Overall response first time point	Overall response subsequent time point*	Confirmed BOR
CR	CR	CR
CR	PR	SD, PD or PR ^a
CR	SD	SD, if minimum criteria for SD duration met at first time point. Otherwise PD
CR	PD	SD, if minimum criteria for SD duration met at first time point. Otherwise PD
CR	NE	SD, if minimum criteria for SD duration met at first time point. Otherwise NE
PR	CR	PR

Overall response first time point	Overall response subsequent time point*	Confirmed BOR
PR	PR	PR
PR	SD	SD
PR	PD	SD, if minimum criteria for SD duration met. Otherwise PD
PR	NE	SD, if minimum criteria for SD duration met. Otherwise NE
NE	NE	NE

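### SAP 10.2.4 sets no end of window for best change in tumour size, so scans taken after new therapy or progression can enter the waterfall plot, unlike the BOR label on the same bars

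*SAP*

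**What the plan says.** SAP 10.2.4 defines three outputs: percentage change in the sum of target-lesion diameters at each scheduled assessment, the best change per subject "based on all post baseline assessments will be summarized descriptively", and the figure: "Waterfall plots will be used to present graphically the largest decrease for each subject by BOR". Reference lines are set at +20% and -30%, with one plot per cohort and one overall. The section gives no date after which scans stop counting. SAP 8.4 adds that unscheduled assessments "will be used in the derivation of endpoints that are not related to a specific timepoint".

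The other scan-based endpoints do have a limit. In SAP 10.2.1 the BOR window closes at the earliest of first documented progression, "the date of non-permitted concomitant treatment, date of a new systemic therapy or the date of study withdrawal for other reason, whichever occurs first". In SAP 10.2.2, subjects who start another anti-cancer therapy before an event are "right-censored at the date of their last adequate tumor assessment prior to initiation of a new anti-cancer therapy", and SAP 10.2.5 has a parallel rule for PFS.

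On data collection before Amendment 2, Protocol 5.1 says: "Disease status will be followed-up every 12 weeks only in subjects without PD from treatment end until PD, death or loss to follow-up". Protocol 8.2.7 repeats this.

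**The concern.** The bar and its label come from different sets of scans. The label (BOR) is closed off when another treatment starts; the length of the bar is not. If a subject stops Debio 1347 without progression, starts another drug and is scanned again, any shrinkage on that drug can become the subject's best change and be displayed as Debio 1347 activity. The error can run in only one direction. A waterfall plot is often the most remembered figure of a single-arm response study, and here there is no control arm against which a reader could judge it.

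**Working it through.** No stated figure in the plan needs reproducing, so the check sets the rules side by side, asks whether later scans can arise, and then works out direction and scale.

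**1. Windows**

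| Output | SAP section | Last scan that counts |
|---|---|---|
| BOR, hence ORR and DCR | 10.2.1, 10.2.3 | First PD, non-permitted treatment, new systemic therapy or withdrawal, whichever is first |
| DOR | 10.2.2 | If new therapy precedes PD or death: last adequate scan before it |
| PFS | 10.2.5 | Same as DOR |
| Best change, waterfall plot | 10.2.4 | None stated |

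Nothing elsewhere in the SAP carries a limit into 10.2.4.

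**2. Can scans outside the BOR window arise?**

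- *After a new therapy.* Protocol 5.1 and 8.2.7 continue disease follow-up off treatment until PD, death or loss to follow-up. Starting another therapy is not among those stopping conditions. SAP section 11 (version 1.0 entry) reads the protocol as following subjects to progression whether or not they are still on drug. So yes, they can.
- *After PD, brain or bone exception.* Protocol 8.4.1 lets some subjects who progress in brain or bone stay on Debio 1347. Scans can follow, but on study drug.
- *After central PD that precedes local PD.* The main analysis uses central reading (SAP 10.2.1.1), while the site decides on treatment. The two readings can differ: SAP Table 6 gives 4 local and 2 central unconfirmed responders in Cohort 1, and 0 and 1 in Cohort 3. Those figures concern response, so it is an inference that PD dates differ too. Such scans would again be mostly on Debio 1347.

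Only the first route credits a later drug. The other two make the bar and its label use different windows.

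**3. Direction**

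Let W be the scans inside the BOR window and L any later ones. As written, best change = min(W and L together), which is never above min(W). Later scans therefore leave the bar unchanged or make it more favourable.

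Illustration with assumed values: scans of -5% and -10% on Debio 1347, then -40% on a later drug.

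- With the cut-off: min(-5, -10) = -10%.
- As written: min(-5, -10, -40) = -40%, which crosses the -30% line.

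**4. Weight of one subject**

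Using the second IDMC sizes in SAP 10.8.2 (30, 4, 29; total 63), one subject is 100/N percentage points:

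- Cohort 1: 100/30 = 3.3
- Cohort 2: 100/4 = 25.0
- Cohort 3: 100/29 = 3.4
- Total: 100/63 = 1.6

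For scale, Table 6 shows 3 unconfirmed central responses in 63 subjects (4.8%). One additional bar beyond -30% would be noticeable in a plot that may have few of them.

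**The case against.** The case for leaving the text alone has five parts.

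- *Meaning of the wording.* SAP 10.2.4 contrasts a by-visit summary on scheduled scans with a best change on all scans, and 8.4 brings unscheduled scans into endpoints of this kind. The wording may mean only scheduled plus unscheduled. That is a plausible intention. But 8.4 treats BOR the same way, and BOR still needed its own cut-off in 10.2.1. A programmer who follows 10.2.4 literally would apply none.
- *Limited opportunity.* Protocol 7.7.3 and 8.4.2 provide for withdrawal when a prohibited medication is needed or used, Amendment 2 ended efficacy collection (Protocol 8.2.2), and SAP section 11 expects perhaps one subject to start new therapy before progression. This stands and keeps the point small. The withdrawal rule does not clearly reach a subject already off drug and in follow-up, and the SAP thought the same rare case worth a censoring rule for DOR and PFS.
- *Progressed subjects.* A reader might infer that a subject with BOR of PD could be credited with a later drug's effect. The documents largely do not support that: off-treatment follow-up excludes subjects with PD and ends at PD, and scans under the brain or bone exception are on Debio 1347.
- *Bar against label.* A reader might also take a bar beyond -30% labelled SD or PD as a contradiction in itself. It is not. Under SAP Table 2, an unconfirmed PR followed by SD becomes SD, and one followed by PD becomes SD or PD depending on the minimum SD duration. Such bars are expected, and a cut-off would not remove them.
- *No inferential role.* Tumour size is descriptive and is not among the listed primary or secondary endpoints. This stands.

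**Conclusion.** The point holds as a gap in a stated rule. Followed literally, SAP 10.2.4 admits scans that every other scan-based efficacy definition in the SAP excludes, and the resulting bias can only favour Debio 1347. It is a minor point. It affects one descriptive summary and its figure, not ORR, DCR, DOR, PFS or any test. The number of subjects cannot be derived from the documents.

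The conclusion assumes that 10.2.4 is programmed as written. For credit to a later drug, it also assumes at least one subject who stopped without PD, started another therapy, was scanned before PD and before Amendment 2 took effect, and reached a new minimum then. A reader might infer that scans under a later drug are already in the database; the documents show only that they can be.

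**What to change.** Add one sentence to SAP 10.2.4: best percentage change and the waterfall plot use scans up to and including first PD, and before any new anti-cancer therapy or other event that closes the BOR window in 10.2.1. Take PD from the same reader as the tumour size shown (central for the main display). Apply the same cut-off to the by-visit summary for consistency, and show later scans in listings only.

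A footnote to the plot could say that bars beyond -30% without a BOR of CR or PR may reflect unconfirmed responses.

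The cost is trivial. Deriving BOR already requires the cut-off dates, and SAP 10.3.7 already lists start dates of anti-cancer therapy after withdrawal. No new data are needed.

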10.2.5 Progression-Free Survival

Progression-free survival (months) is defined as (date of the first documented disease progression or death due to any cause, whichever occurs first - start date of treatment + 1)/30.4375.

The following censoring rule will be applied:

- Subjects who do not experience death or PD, nor initiate anti-cancer therapy will be right-censored at the date of their last adequate tumor assessment (i.e. a tumor assessment not showing NE).
- Subjects having initiated a new anti-cancer therapy before experiencing death or PD will be right-censored at the date of their last adequate tumor assessment prior to initiation of a new systemic therapy.
- Subjects who experienced death or PD after two or more consecutive missing or inadequate tumor assessments will be right-censored at their latest adequate assessment before death or PD.
- Subjects without a baseline or post-baseline assessment will be right-censored at the date of first administration of the study drug.

Progression-free survival rate at every 6 months will be presented with the corresponding 95% CIs will be estimated using the K-M method. A K-M plot for PFS will be presented.

The analysis will be performed on PFS calculated based on IRC assessment of response on the ITT population as the main analysis. Supportive analyses will be performed using:

- IRC evaluation of response on mITT and PP populations.
- Investigator assessed response on ITT, mITT and PP populations.

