### 8.3. Study Procedures and Plan

Assessments are described in detail in Section 8.2. A study plan including timing of tests and evaluations is presented below in Table 8-1.

All eligible subjects will attend the study visits indicated in the study plan. Study procedures must be performed according to the planned time schedule with strict adherence to visit intervals.

Prior to conducting any of the screening tests, the Investigator or his/her designee will explain the study fully to the prospective subject and provide him/her with a copy of the Patient Information Leaflet/Informed Consent Form for the entire study. If the subject is willing to participate in the study, s/he and the Investigator or his/her designee will each sign two copies of the Informed Consent Form of which the subject keeps one.

Subjects who are confirmed at the pre-screening assessment as harboring FGFR fusions/rearrangements (see Section 8.2.1.1) will attend the full screening visit within 28 days prior to the first treatment cycle. Subject suitability will be confirmed by the inclusion/exclusion criteria in Section 6. A subject may be re-screened on the conditions described below.

**Of note:** Subjects who require a central assessment of FGFR status (pre-screening test, see Section 8.2.1.1) will be asked to sign a pre-screening Informed Consent Form to this intent.

As per Protocol Amendment N° 2, the updated study plan is presented in Table 8-1b.

All subjects will be followed by the Investigator as per standard institutional care practice. Subjects will receive Debio 1347 for as long as they are benefitting from the study drug and there is no safety concern as per Investigator's judgment. Pregnancy, AEs, AESI, SAEs, will be documented and collected in the study eCRF, and reported using dedicated forms described in section 9.2 of this protocol.

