#### **11.5.6.2. Secondary efficacy endpoints**

Disease control rate is defined as the proportion of subjects with a BOR of CR, PR or SD. Disease control rate will be summarized by cohort and overall using frequencies and percentages. The 95% clopper Pearson CI will be presented overall and by cohort.

Duration of response is defined as the time from the date of the first documented PR or CR to date of the first documented disease progression or death due to any cause, whichever occurs first. It will be calculated only for subject with a best overall response of CR or PR.

Progression-free survival is defined as the time from the start date of treatment to date of the first documented disease progression or death due to any cause, whichever occurs first. It will be expressed in months.

The following censoring rules will be applied on PFS and DOR for subject with no documented disease progression or death:

- Subjects who do not experience death or PD, nor initiate a new anti-cancer therapy will be right-censored at the date of their last adequate tumor assessment (i.e. a tumor assessment not showing NE).
- Subjects having initiated a new anti-cancer therapy before experiencing death or PD will be right-censored at the date of their last adequate tumor assessment prior to initiation of a new anti-cancer therapy.
- Subjects who experienced death or PD after two or more consecutive missing or inadequate tumor assessments will be right-censored at their latest adequate assessment before death or PD.

Overall survival is defined as the time from the start date of treatment to date of death due to any cause. Subjects with no documented death will be censored at the last date known to be alive.

Duration of response, PFS and OS will be summarized using the Kaplan Meier method. Median survival time and the associated CI will be estimated. Duration of response rate and PFS rate at 6 month and 1 year, and OS rate at 1 year and 2 years and the corresponding CIs will be estimated using the Kaplan Meier method.

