3.2 Secondary Endpoints

The secondary endpoints are:

1. DOR, defined as the time from the date of the initial partial response (PR) or complete response (CR) to date of the first documented progressive disease (PD) or death due to any cause.
2. DCR, defined as the proportion of subjects with a BOR of CR, PR or SD .
3. PFS, defined as the time from the start date of treatment to date of the first documented PD or death due to any cause.
4. OS, defined as the time from the start date of treatment to date of death due to any cause.
5. Proportion of subjects with treatment-emergent adverse events (TEAEs) assessed by the National Cancer Institute - Common Terminology Criteria for Adverse Events (NCI-CTCAE) v5.0 and proportion of subjects with serious adverse events (SAEs).
6. Debio 1347 plasma exposure (C_{trough} , area under the curve [AUC $_{\tau}$] and any other PK parameters as deemed appropriate) and relationships with efficacy and safety endpoints; Debio 1347 plasma concentration (C)-QTcF relationship based on electrocardiogram (ECG) and PK matching time-points. These relationships will be derived only if deemed appropriate, depending on the safety and efficacy outcomes and data availability.

■ [REDACTED]

■ [REDACTED]

■ [REDACTED]

■ [REDACTED]

■ [REDACTED]

■ [REDACTED]

■ [REDACTED]

■ [REDACTED]

■ [REDACTED]

■ [REDACTED]

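### SAP 10.2.5 may censor at first dose a death before any post-baseline scan that the PFS definition counts as an event; the wording is ambiguous and any effect is probably small

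*SAP*

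**What the plan says.** SAP 3.2 gives the endpoint as "PFS, defined as the time from the start date of treatment to date of the first documented PD or death due to any cause", and SAP 10.2.5 repeats it as a formula in months. Neither requires a scan before a death can count.

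SAP 10.2.5 then lists four censoring bullets under a stem that is not limited to subjects without an event:

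- Bullet 1: no death, progression or new therapy. Censor at the last adequate assessment.
- Bullet 2: "Subjects having initiated a new anti-cancer therapy before experiencing death or PD will be right-censored at the date of their last adequate tumor assessment" (the last one before that therapy).
- Bullet 3: "Subjects who experienced death or PD after two or more consecutive missing or inadequate tumor assessments will be right-censored at their latest adequate assessment".
- Bullet 4: "Subjects without a baseline or post-baseline assessment will be right-censored at the date of first administration of the study drug".

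Protocol 11.5.6.2 contains only the first three, introduced by: "The following censoring rules will be applied on PFS and DOR for subject with no documented disease progression or death". It has no counterpart to bullet 4, although SAP section 1 says that the SAP complies with protocol version 3.

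The SAP foresees early deaths without a scan. In SAP 10.2.1, "Patients who die with no evaluable RECIST assessments will be assigned to the NE category". In SAP 10.2.1.1 the NE category has a sub-row for "death without post-baseline assessment". The PFS section has no matching provision.

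**The concern.** A subject who dies early without a post-baseline scan has had a PFS event by definition. Bullet 3 points the same way: it censors a death only after at least two consecutive missing or inadequate assessments, which implies that a death after none or one is an event. Bullet 4, read as covering anyone who lacks either a baseline or a post-baseline assessment, takes that subject out of the risk set at first dose instead.

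Two things are at stake. A failure would become a non-informative Day 1 censoring in the reported PFS rates. And because the wording has more than one reading, the result could depend on who programs it.

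**Working it through.** The plan states no PFS rate, PFS event count or number of early deaths, so there is no figure to reproduce. The check covers which deaths are affected, the direction and the size.

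**1. Deaths that bullet 4 alone would change.** An unscanned death after new therapy, or after two missed assessments, is already censored by bullets 2 or 3. What remains is an unscanned death with no new therapy and fewer than two consecutive missed assessments. ITT and mITT (SAP 7.2, 7.3) keep such subjects. PP does not, because SAP 7.4 requires a post-baseline assessment. ORR, DCR and OS do not use this bullet.

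**2. When such deaths can occur.** On treatment, scans fall at the end of Cycles 2, 4 and 6 (Days 56, 112, 168), then every 3 cycles (Protocol 8.2.2.1.2). The second missed scan is therefore at about Day 112, before the 6-month landmark (6 × 30.4375 = 182.6 days). Off treatment without progression, disease status is assessed every 12 weeks from last dose (Protocol 8.2.7). Take a last dose on Day 20 and no scan. If the end-of-treatment (EOT) scan counts as scheduled, the second miss is at about Day 20 + 84 = 104. If only the 12-weekly visits count, it is at Day 20 + 168 = 188, which is after the landmark.

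**3. Direction for a death before the landmark.** Let n be all subjects, k such deaths, and s the number event-free at the landmark.

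- With no other censoring: counted as events, S = s/n; under bullet 4, S = s/(n−k). The ratio is n/(n−k).
- With other censoring: write f(Y) = Y/(Y+m), where Y is the number of other subjects at risk and m the number of the k still at risk. The ratio of the counted to the bullet 4 estimate telescopes to (n−k)/n times terms that are at most 1, one for each time another subject is censored. So n/(n−k) is the minimum inflation.
- Numerical check for one death on Days 2–111: 12,000 comparisons at 6 and 12 months. The rate rose in all of them except 786 in which it was already 0.

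**4. Size, on assumed inputs.** SAP 9.3 gives 63 evaluable subjects, 30 of them in Cohort 1. SAP 10.8.1 defines evaluable as having a post-baseline assessment or having progressed, so k is added to these. The true 25% rate is assumed. Half-width = 1.96 × √(0.25 × 0.75/n).

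| Set | k | Factor | 25% becomes | 95% half-width |
|---|---|---|---|---|
| Pooled | 1 | 64/63 = 1.016 | 25.4% | 10.6 points |
| Pooled | 3 | 66/63 = 1.048 | 26.2% | 10.4 points |
| Cohort 1 | 1 | 31/30 = 1.033 | 25.8% | 15.2 points |
| Cohort 1 | 3 | 33/30 = 1.10 | 27.5% | 14.8 points |

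**5. Direction for a death after the landmark.** Suppose 20 of 63 are event-free at 6 months, including one subject who dies unscanned on Day 185 and whom bullet 3 does not catch. Counted: 20/63 = 31.7%. Under bullet 4: 19/62 = 30.6%. The 6-month rate falls.

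**6. Median.** Take 63 subjects, 31 progressing on Day 56 and 3 dying unscanned on Day 100. Counted: S(56) = 32/63 = 0.508 and S(100) = 29/63 = 0.460, so the median is Day 100 (3.29 months). Under bullet 4: S(56) = 29/60 = 0.483, so the median is Day 56 (1.84 months), which is lower. In a simulation (n = 66, k = 3, deaths uniform over Days 2–111, assumed latent median 2.0 months), the median was unchanged in about 79% of runs, higher in 19% and lower in 1.3%. It can move either way, and so can Q1.

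**7. If bullet 4 means lacking both assessments.** Inclusion criterion 7 (measurable disease) leaves that group almost empty. Unscanned, event-free subjects then fall to bullets 1–2, with the screening scan as their last adequate assessment. Protocol 8.3 says subjects "will attend the full screening visit within 28 days prior to the first treatment cycle". The SAP formula gives (−28 + 1)/30.4375 = −0.89 to (−1 + 1)/30.4375 = 0 months, which is not a usable time. The "either" reading therefore gives the bullet a purpose, but the text does not settle the matter.

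**The case against.** The strongest reply is that bullet 4 was meant only for subjects with no event. The protocol's stem says so, the SAP claims to follow the protocol, and on that reading the bullet still prevents zero or negative times without removing any death. This is a fair reading and shows that censoring of deaths is not certain. It does not rescue the text. The SAP drops the stem's restriction, and bullet 3 explicitly censors some deaths under the same stem, in both documents. A programmer cannot assume that a recorded death overrides the list.

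It is also true that a reader of the report could see whether the case arose: early unscanned deaths have their own best-response sub-row, all deaths are listed (SAP 10.3.2), events and censorings are counted (SAP 9.1), and OS includes these deaths. That limits the harm but does not correct the PFS estimate.

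A reader might infer more: that every death before a first scan inflates every PFS rate and the median. The documents do not support that. Bullets 2 and 3 already censor some of these deaths. The mITT estimate moves only if the subject belongs to mITT. An estimate already at 0 cannot rise. A death after a landmark lowers the rate there, and the median can go either way. Nor can it be inferred that the trial's PFS is in fact overstated, because no such death is documented.

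**Conclusion.** The point holds as a minor one. In its most natural reading, bullet 4 may turn into a Day 1 censoring a death that the SAP's PFS definition counts as an event and that, where bullets 2 and 3 do not apply, the protocol counts too. The minimum inflation, n/(n−k), applies to deaths before the landmark under any pattern of other censoring. The percentages are illustrations only: the ITT size, k, the true rate and the death times are not in the documents.

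There is reason to expect k to be small. Entry requires a life expectancy of at least 3 months, and a scan is due at progression and/or end of treatment. In the Phase I dose escalation (Protocol 3.3.2), all 57 evaluable subjects had a best response of progression, stable disease or partial response. At the sizes shown, the shift is well inside the confidence interval, and PFS is a secondary endpoint with no hypothesis test. The ambiguity is worth removing even if k is zero.

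**What to change.** Reword bullet 4 along these lines: *A subject lacking a baseline assessment, or lacking every post-baseline assessment, is censored at first dose, unless the subject died before two consecutive scheduled tumor assessments had been missed and before any new anti-cancer therapy; that death is a PFS event on its own date.*

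Then add:

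- which assessments count as scheduled (on-treatment, EOT and 12-weekly follow-up scans), with the same definition used in bullet 3;
- that bullet 4 takes precedence over bullets 1–3 for subjects lacking either a baseline or any post-baseline assessment, so that no censoring date falls before first dose;
- a table row giving the number censored at first dose, with their vital status.

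The cost is one reworded bullet, two clarifying sentences, a small programming change and one table row. If such deaths occurred before 6 months, the reported PFS rates become slightly lower. No data collection or clinical procedure changes.
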